Registry Objective	The primary objective is to confirm the clinical performance of the [REDACTED] when used as a Bridging Stent with Branched and Fenestrated Endografts in the Treatment of Aortic Aneurysms involving the Renal-Mesenteric Arteries. The secondary objective is to confirm safety of the [REDACTED] when used as a Bridging Stent with Branched and Fenestrated Endografts in the Treatment of Aortic Aneurysms involving the Renal-Mesenteric Arteries.
Registry Endpoint(s)	Target vessel patency (patient level) at 12 months
Subject Population	Patients treated with the [REDACTED] as a Bridging Stent in conjunction with a branched/fenestrated stent-graft to allow endovascular aneurysm repair
Inclusion Criteria	
 1. Patients treated with the [REDACTED] as a Bridging Stent in conjunction with a branched/fenestrated stent-graft to facilitate endovascular aneurysm repair from 31 December 2021 until 01 January 2017 2. Age \geq18 years at the time of implant

CONFIDENTIAL INFORMATION

	3. An Informed Consent Form (ICF) signed by subject or next of kin/legal representative (for deceased patients at registry entry, unless a waiver was granted), according to local regulations.												
Exclusion Criteria	
 1. Patient treated for ruptured aneurysm or who were otherwise hemodynamically unstable at the time of the procedure 2. Patient treated for acute or subacute dissection, <90 days from onset of symptoms 3. Patient treated using physician-modified endovascular grafts 4. Patient intended to be treated with chimney, periscope, octopus, sandwich technique per the pre treatment case plan. 5. At the time of treatment, patient had known coagulation disorders including hypercoagulability that were not amenable to treatment 6. Patient was pregnant at the time of treatment. 7. Participation in another drug or device investigational study within one year of device implant, that can confound the registry endpoints. 8. Patient had known or suspected systemic infection (including treatment for mycotic aneurysm) at the time of implant. 												
Number of Subjects	
  
 Subject Cohort	Number patients	Caps per site (patient)	
   
 Fenestrated repair (FEVAR)	100	First cap 10% (10 patients) Second and max Cap 30% (30 patients)	
 
 Branched repair (BEVAR)	120	First cap 10% (12 patients) Second and max Cap 30% (36 patients)	
 
 Fenestrated-branched repair	Up to 40	N.A.	
  
	Subject Cohort	Number patients	Caps per site (patient)	Fenestrated repair (FEVAR)	100	First cap 10% (10 patients) Second and max Cap 30% (30 patients)	Branched repair (BEVAR)	120	First cap 10% (12 patients) Second and max Cap 30% (36 patients)	Fenestrated-branched repair	Up to 40	N.A.
Subject Cohort	Number patients	Caps per site (patient)											
Fenestrated repair (FEVAR)	100	First cap 10% (10 patients) Second and max Cap 30% (30 patients)											
Branched repair (BEVAR)	120	First cap 10% (12 patients) Second and max Cap 30% (36 patients)											
Fenestrated-branched repair	Up to 40	N.A.											
Number of Sites	Up to 15 sites in Europe												
Coordinating PI	
[REDACTED]
 
Contact details and professional position are kept separately from this protocol
												
Registry Duration	
Time to complete enrollment: 8 months, all subjects are enrolled retrospectively
 
Follow-up time: FU data collection up to 5 years. Part of the FU will be prospective.
 
Total registry duration: 5.5 years
												

CONFIDENTIAL INFORMATION

Additional Information	Contract Research Organization (CRO): [REDACTED] [REDACTED] [REDACTED] [REDACTED]
	Electronic Data Capture System: [REDACTED] [REDACTED] [REDACTED]
	Core Lab: [REDACTED] [REDACTED] [REDACTED] [REDACTED]
	Imaging Transfer: [REDACTED] [REDACTED]

CONFIDENTIAL INFORMATION

MD133246 Protocol Template

Revision#: 7

Doc Type: GC

Page iv

LIST OF ABBREVIATIONS

AE	Adverse Event
ADE	Adverse Device Effect
ASA	American Society of Anesthesiologists
BEVAR	Branched endovascular aneurysm repair
CAAA	Complex abdominal aortic aneurysms
CABG	Coronary Artery Bypass Graft
CAD	Coronary Artery Disease
CBC	Complete Blood Count
CDMS	Clinical Data Management System
CE	Conformité Européenne
CEC	Clinical Events Committee
CFR	Code of Federal Regulations
CIP	Clinical Investigation Plan
cm	Centimeters
CRF	Case Report Form
CRO	Contract Research Organization
CT	Computed Tomography
CTA	Computed Tomographic Angiography
DTA	Descending Thoracic Aortic
EC	Ethics Committee
EDC	Electronic Data Capture
eCRF	Electronic Case Report Form
ePTFE	Expanded Polytetrafluoroethylene
ESVS	European Society for Vascular Surgery
EU	European Union
FEVAR	Fenestrated endovascular aneurysm repair
FDA	Food and Drug Administration (United States)
Fr	French (sizing)
GCP	Good Clinical Practice
GIS	Gore Imaging Sciences
HE	Health Economics
ICF	Informed Consent Form
ICH	International Conference on Harmonization

CONFIDENTIAL INFORMATION

IFU	Instructions for Use
LAR	Legal Authorized Representative
LSA	Left Subclavian Artery
MDD	Medical Devices Directive
MDR	Medical Devices Regulation
MI	Myocardial Infarction
mm	Millimeters
MRI	Magnetic Resonance Imaging
OMA	Office of Medical Affairs (W. L. Gore & Associates, Inc.)
PG	Performance Goal
PHI	Protected Health Information
PI	Principal Investigator
SAE	Serious Adverse Event
SVS	Society of Vascular Surgery
TAAA	Thoraco-Abdominal Aortic Aneurysms
TIA	Transient Ischemic Attack
USADE	Unanticipated Serious Adverse Device Effect

CONFIDENTIAL INFORMATION

DEFINITIONS

Adverse Event: Untoward medical occurrence, unintended disease or injury, or untoward clinical signs (including an abnormal laboratory finding) in subjects, users, or other persons, whether or not related to the investigational medical device whether anticipated or unanticipated. This definition includes events related to the investigational medical device and events related to the procedures involved

Adverse Device Effect: Adverse event related to the use of an investigational medical device

Clinical Investigation Plan: A set of documents that describes the rationale, objectives, design and proposed analysis, methodology, monitoring, and the plan for the conduct of a clinical investigation. These documents may include the protocol, monitoring plans, and statistical analysis plans.

Device Deficiency: Any inadequacy in the identity, quality, durability, reliability, safety, or performance of an investigational device, including malfunction, use errors, or inadequacy in information supplied by the manufacturer.

Enrollment: A patient is considered enrolled into the registry once informed consent has been signed and dated or consent is waived.

Registry Device: The medical device being assessed for safety or performance in this registry. May also be referred to as registry device. This includes medical devices already on the market that are being evaluated for new intended uses, new populations, new materials, or design changes.

Serious Adverse Event: Any adverse event that led to any of the following:

- (a) death
- (b) serious deterioration in the health of the subject, users, or other persons as defined by one or more of the following:
 - (i) life-threatening illness or injury,
 - (ii) permanent impairment of a body structure or a body function including chronic diseases,
 - (iii) in-patient or prolonged hospitalization,
 - (iv) medical or surgical intervention to prevent life-threatening illness or injury or permanent impairment to a body structure or a body function
- (c) fetal distress, fetal death, or a congenital abnormality, or birth defect including physical or mental impairment

Defined in more detail in section 9.1.2.

Serious Adverse Device Effect: An adverse device effect that has resulted in any of the consequences characteristic of a serious adverse event

Serious Health Threat: Signal from any adverse event or device deficiency that indicates an imminent risk of death or a serious deterioration in the health in subjects, users or other persons, and that requires prompt remedial action for other subjects, users or other persons.

Unanticipated Adverse Device Effect: Any serious adverse effect on health or safety or any life-threatening problem or death caused by, or associated with, a device, if that effect, problem, or death was not previously identified in nature, severity, or degree or incidence in the investigational plan or application (including

CONFIDENTIAL INFORMATION

a supplementary plan or application), or any other unanticipated serious problem associated with a device that relates to the rights, safety, or welfare of subjects.

Unanticipated Serious Adverse Device Effect: Serious adverse device effect which by its nature, incidence, severity, or outcome has not been identified in the current version of the protocol and IFU.

CONFIDENTIAL INFORMATION

MD133246 Protocol Template

Revision#: 7

Doc Type: GC

Page viii

Table of Contents

PROTOCOL SUMMARY.....	ii
LIST OF ABBREVIATIONS.....	v
DEFINITIONS.....	vii
1. Introduction.....	1
1.1. Disease.....	1
1.2. Historical Treatments	1
1.3. Registry Device Description	2
1.4. Pre-clinical Data.....	3
1.5. Clinical Data	3

1.1. Disease

Complex abdominal aortic aneurysms (CAAAs) and thoraco-abdominal (TAAAs) are those that affect the visceral aortic branch vessels (including the renal, the celiac trunk and the superior and inferior mesenteric arteries).¹ CAAAs (including short-necked infrarenal juxtarenal, paravisceral and suprarenal aneurysms) are defined as aneurysms that involve the renal or mesenteric arteries and extend up to the level of the celiac axis or diaphragmatic hiatus but do not extend into the thoracic aorta.² Aneurysms extending proximal to the renal arteries which involve variable extent of the thoracic aorta are referred to as TAAAs which were classified by Crawford-Safi based on the extent of surgical repair required. EVS guidelines³ provide anatomic descriptions which are included in Table 1.

Table 1. TAAA Classification per EVS Treatment Guidelines

TAAA Type	Definition ³
Type I	Start at the level of the left subclavian artery, or at least proximal to the level of the sixth vertebra (T6) and affect the entire DTA, involve the visceral arteries and end at the renal arteries. The aneurysm can involve the origin of the LSA or even involve the distal aortic arch.
Type II	Start at the same level as a type I, but involve the DTA and the entire abdominal aorta
Type III	Start more distal than type II aneurysms, usually at the level of T6, and extend distally as in a type II.
Type IV	Start at the level of the diaphragm and involve the entire abdominal aorta, with or without extension to the iliac arteries.

1.2. Historical Treatments

CAAAs and TAAAs involving the visceral segment may be treated by open surgical repair specific to the type of aneurysms or a variety of endovascular techniques. The purpose of this registry is to assess the utility of the [REDACTED]

[REDACTED] as a bridging stent when used in conjunction with a branched or fenestrated stent graft. Therefore, this review will focus on the devices that are used in this application.

In early experience with fenestrated grafts, bare metal stents were commonly employed primarily to maintain alignment of the fenestration with the target vessel. As an example, the Cook Zenith® fenestrated graft study reported a mixed usage of bare metal and covered stents in the bridging application.⁴ In this report, loss of patency was higher in vessels treated with bare metal stents, although this was not statistically significant. Over time, balloon expandable covered stents have become the preferred option for FEVAR. More recently, Farivar and colleagues published results with a variety of devices and conclude that the choice of balloon expandable covered stent has no effect on branch durability in FEVAR procedures.⁵

CONFIDENTIAL INFORMATION

In BEVAR procedures, a covered bridging stent is generally selected given the need to exclude the aneurysm from circulation while still maintaining perfusion of the target vessel. Mastracci and colleagues⁶ performed an analysis of outcomes in branched aortic repair and were unable to demonstrate any difference in occlusion or reintervention between balloon-expandable and self-expandable covered stents.

[figure not shown]
The successful usage of the [REDACTED] has been reported in several publications involving FEVAR and BEVAR procedures⁷⁻¹¹, which suggests that this device may offer a reasonable option as a bridging stent in these applications.

1.3. Registry Device Description

The design, device sizes, and characteristics permit the use of the device in multiple pathologies.

CONFIDENTIAL INFORMATION

1.4. Pre-clinical Data

Gore has performed the following pre-clinical testing on the [REDACTED]

1.5. Clinical Data

More detailed device information can be found in the Instructions for Use (IFU)

2. Registry Objectives

2.1. Primary Objective(s)

The primary objective is to confirm the clinical performance of the [REDACTED] [REDACTED] when used as a Bridging Stent with Branched and Fenestrated Endografts in the Treatment of Aortic Aneurysms Involving the Renal-Mesenteric Arteries.

CONFIDENTIAL INFORMATION

2.2. Secondary Objective(s)

[figure not shown]
The secondary objective is to confirm safety of the [REDACTED] when used as a Bridging Stent with Branched and Fenestrated Endografts in the Treatment of Aortic Aneurysms involving the Renal-Mesenteric Arteries.

2.3. Health Economic Data Analysis

A Health Economic analysis will be performed using clinical registry data. The objective of the Health Economic analysis is to understand the value of the treatment(s) studied during the period of the registry.

3. Registry Design

3.1. Registry Design Schema

CONFIDENTIAL INFORMATION

3.2. Description of Registry Design

This multicenter, single-arm retrospective and prospective registry is being conducted to confirm the clinical performance and safety of [REDACTED] when used as a Bridging Stent with Branched and Fenestrated Endografts in the Treatment of Aortic Aneurysms Involving the Renal-Mesenteric Arteries.

A single arm design was chosen as the clinical application does not readily lend to randomization due to involvement of multiple vessels and variability with respect to the main body design.

A retrospective and prospective registry was determined to be suitable observational study design to reliably answer the research question, based on consistency of device design, procedures, clinical results available and operative techniques.

Up to 15 sites in Europe will be required to enroll a minimum of 220 patients that have had treatment with [REDACTED] when used as a Bridging Stent with Branched and Fenestrated Endografts in the Treatment of Aortic Aneurysms Involving the Renal-Mesenteric Arteries.

Each site cannot contribute to more than 10% of the total patient for each cohort without sponsor approval, with a maximum of 30% of total enrollment for a single site. See section 4.1 for more details.

The Sponsor or designee will maintain an updated list of all principal investigators, site names, and addresses. This list shall be kept separately from this protocol.

Subjects may be enrolled when all inclusion and no exclusion criteria are met as specified in section 4.2. Patients are enrolled into the registry when they provide consent or consent is waived and meet all inclusion and exclusion criteria.

Subjects' medical records will be reviewed by the investigator and specific data will be collected retrospectively and prospectively for up to 5 years of follow-up from the index procedure.

3.3. Management of potential confounding factors / bias

Bias will be controlled by strict adherence to the registry protocol. Sites will be monitored for compliance with registry protocol, including subject eligibility criteria, as allowed by EC regulations. In order to minimize selection bias, it is mandatory that the enrollment of patients will be consecutive in nature based on the date of the index procedure. Gore has put in place quality control to ensure that no selection bias is applied by the site during patient screening, please see section 5.5 for more details.

The registry is meant to retrospectively and prospectively collect data for reporting as well as evaluate "real world" experience of clinical practice and patient outcomes during treatment and throughout follow-up extending up to 5 years. Patient selection, diagnostic imaging and treatment interventions will be determined by physicians based on this protocol and clinical practice standards.

CONFIDENTIAL INFORMATION

It is well known that excluding treated patients who are deceased or not reachable at the time of the inclusion due lack of informed consent can generate an important selection bias in retrospective study and is likely to seriously prevent the achievement of the research objectives. Therefore, for patients, who are deceased or not reachable at the time of the inclusion, the consent can be waived, signed by next of kin/legal representative, according to local regulations.

Refer to section 5.3.1 regarding the waived process.

3.4. Registry Endpoint(s)

3.4.1. Definitions

Outcome	Definition per SVS reporting Standards
Technical Success Related Outcomes	
Target Vessel Technical Success	
Successful catheterization and [REDACTED] placement in all intended target vessels.
 
For this registry, technical success will be reported for the overall procedure and specifically for the vessels targeted for treatment with the [REDACTED]

Primary Technical Success (Total Endovascular Procedure)	
A modified technical success definition, requiring the following:
 
 1. Successful side branch catheterization and placement of bridging stents with restoration and maintenance of flow in all intended target vessels 2. Patency of all aortic modular stent graft components and intended side branch components 3. Absence of type I or type III endoleaks at completion angiography that extends beyond 30 days by confirmatory imaging (CTA, magnetic resonance angiography [MRA], or duplex ultrasound)
Vessel Patency Related Outcomes	
Primary Patency (Primary Endpoint)	Uninterrupted patency with no occlusion or procedure performed to maintain patency on the [REDACTED] stent or native target vessel. Interventions intended to treat endoleak or stent disconnection do not count as loss of primary patency.
Primary Assisted Patency	Endovascular intervention performed to maintain patency in the presence of a stenosis before occlusion

CONFIDENTIAL INFORMATION

Secondary Patency	Endovascular restoration of patency after occlusion of the side branch, stent, or stent graft has already occurred. Conversion to bypass or inability to treat by endovascular means defines loss of secondary patency
Occlusion	Objective documentation by angiography, computed tomography, or ultrasound of complete stent occlusion with or without minimal flow into a targeted vessel
Stenosis	Objective documentation by angiography, computed tomography, or ultrasound of stenosis intra-stent or into a targeted vessel
Kink	Objective documentation by angiography, computed tomography, or ultrasound of kink in the stented or native segment of a targeted vessel
Other Outcomes	
Intraprocedural complications	Any vessel perforation, dissection, or occlusion during target vessel stenting
Reintervention	
Any repeated vascular or nonvascular procedure related to the index procedure
 
Reintervention will be adjudicated as major or minor based on the following
 
Major: deployment of proximal or distal aortic or iliac extensions, removal of the device, use of thrombectomy or thrombolysis, and any major open surgical procedure.
 
Minor: endovascular procedures (percutaneous transluminal angioplasty, atherectomy, stenting) without thrombectomy or thrombolysis, interventions to treat branch vessel stenosis, interventions to treat type II endoleak or branch-related endoleaks, and minor surgical revisions (patch angioplasty) of the access vessels.
 
Each reintervention will be adjudicated as related to a [REDACTED]-treated branch vessel component, related to a non-[REDACTED]-treated branch vessel component, or related to main body component(s), if possible.

Target vessel instability	Death or rupture related to side branch complication (e.g., endoleak) or reintervention to treat a branch-related complication, including endoleak, disconnection, kink, stenosis, occlusion, or rupture

CONFIDENTIAL INFORMATION

Aneurysm-related mortality	Any death that occurs within the first 30 days or any death that results from aneurysm rupture, aorta-related complications (eg, infection, occlusion, dissection, hematoma), or a complication of a secondary intervention
Major Adverse Events (MAEs)	
All-cause mortality
 
Myocardial infarction (MI): MI resulting in severe hemodynamic dysfunction necessitating resuscitation, cardiac arrest, or fatal outcome.
 
Respiratory failure requiring prolonged (>24 hours from anticipated) mechanical ventilation or reintubation
 
Any renal function deterioration according to the RIFLE classification system.
 
Bowel ischemia requiring surgical resection or not resolving with medical therapy
 
Permanent paraplegia (any grade 3 A-C spinal cord injury) in a patient who is no ambulatory.
 
Any major stroke defined according to National Institutes of Health Stroke Scale (NIHSS) or equivalent.

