3.4.2. Primary Endpoints

- Primary Performance Outcome: Target vessel patency (patient level) at 12 months

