5.15. Explant Procedures

The [REDACTED] may be explanted during a surgical procedure or as part of an autopsy. If this occurs during the prospective phase of the registry sites are requested to return explanted devices to the sponsor for gross and histological evaluation. Prior to planned or potential device retrieval, contact the Gore Associate managing the registry to communicate that a specimen is being retrieved from a registry subject. A specimen shipping kit will be immediately sent to the site. The specimen kit provides specific packaging and handling instructions for the specimen and contains a shipping container.

In complex aortic procedures it is expected that more than one [REDACTED] can be implanted in the same subject, if the explanted device is the only one used in the subject then the subject will be discontinued, if other [REDACTED] remain implanted the subject will continue in the registry.

6. Registry Administration

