9.1.4. Subject Death

In this registry, death is not considered an AE, but rather the outcome of an AE. An ongoing AE at the time of death or registry withdrawal will remain categorized as ongoing.

Attempts will be made by the Site to obtain death certificate and autopsy reports, when possible.

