10.1. Registry Hypotheses

The registry is designed to statistically test the hypothesis that the Target Vessel Patency at 12 months (Primary Performance Endpoint) in both FEVAR and BEVAR populations of subjects is greater than 77%. The hypothesis will be tested separately in the two cohorts (FEVAR and BEVAR), using the subjects with imaging results available for the 12 months visit. The binomial exact test will be used with a one-sided 2.5% level of significance to test the null hypothesis.

The statistical hypothesis is specified as follows:

$H_0: P < 77\%$

$H_A: P \geq 77\%$

Alpha= 0.025 (one-sided)

Whereas P is the probability of maintaining Target Vessel Patency at 12 months.

The ITT population will be used to perform this test.

A separate analysis in the subgroup with mixed placement of branched and fenestrated endografts as well as other clinical uses not described as only FEVAR or BEVAR will also be assessed with no formal hypothesis.

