Analysis of the Primary Endpoint to test the hypothesis will be performed using binomial exact test using one-sided 2.5% level of significance.

All subjects with follow-up visit and imaging results available from 9 to 15 months will be included in the primary analysis. Subjects with the loss of Target Vessel Patency earlier than 15 months will also be included in such analysis and considered as failures regardless of the timing and availability of another visit between 9 to 15 months.

[REDACTED]

Statistical Analysis of Secondary Endpoint(s)

[REDACTED]

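### A fatal target-vessel occlusion shown only at autopsy, or at surgery with no procedure on the vessel, leaves the primary patency analysis instead of counting as a failure

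*Protocol*

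**What the plan says.** The primary endpoint is patient-level target vessel patency at 12 months (Protocol 3.4.2), tested against 77% in each cohort separately by a one-sided exact binomial test at 2.5%.

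- **How patency is lost.** Protocol 3.4.1 defines primary patency as "Uninterrupted patency with no occlusion or procedure performed to maintain patency on the" study stent or native target vessel. There are two routes to failure: an occlusion, or a procedure to maintain patency.
- **What counts as an occlusion.** It is a defined term: "Objective documentation by angiography, computed tomography, or ultrasound of complete stent occlusion". SAP Table 1 repeats it. Autopsy, explant and operative findings are not listed. The procedure route carries no imaging condition.
- **Who is analysed.** Protocol 10.1 tests "using the subjects with imaging results available for the 12 months visit". SAP 5.0 states: "All subjects with follow-up visit and imaging results available from 9 to 15 months will be included in the primary analysis". The SAP then adds, as failures, subjects who lost patency before 15 months, whether or not they have a visit in the window. Missing data are not imputed (Protocol 10.4.5; SAP 4.0).
- **What is gathered on deaths.** Protocol 9.1.4: "Attempts will be made by the Site to obtain death certificate and autopsy reports, when possible". Protocol 5.15 notes that the device "may be explanted during a surgical procedure or as part of an autopsy" and asks for its return if this happens in the prospective phase. Target vessel instability, a secondary endpoint, includes "Death or rupture related to side branch complication (e.g., endoleak) or reintervention to treat a branch-related complication".

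**The concern.** Consider a patient who dies at month 2 of bowel ischaemia from an occluded bridging stent. No angiogram, CT or ultrasound shows the occlusion. It is found at autopsy, or at a laparotomy where the surgeon does nothing to the stent or vessel. The patient has no window imaging, no occlusion as defined and no patency procedure, so neither entry rule applies and the patient leaves the denominator. The same happens to a death after month 9 that comes before any window imaging.

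A clear failure of the device is then dropped, and dropping it can only raise observed patency. Such deaths are reported elsewhere: in target vessel instability, in aneurysm-related mortality where that definition is met, and within 30 days among the major adverse events. None of these enters the 77% test.

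The omission also runs against the protocol's own aim. Protocol 3.3 warns of selection bias if deceased patients are left out for lack of consent, and allows waivers to keep them. Imaging follows routine practice and much of the follow-up is retrospective, so listed imaging before an early death cannot be assumed.

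**Working it through.** **Step 1. Trace the patient through the rules.**

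| Situation before any window imaging | Occlusion as defined? | Patency procedure? | Primary analysis |
|---|---|---|---|
| Occlusion on angiography, CT or ultrasound, then death | Yes | Not needed | Failure |
| Occlusion found at surgery and treated to restore flow | Not needed | Yes | Failure |
| Occlusion found at surgery, nothing done to stent or vessel, death | No | No | Not in the analysis |
| Occlusion found only at autopsy | No | No | Not in the analysis |

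The gap is the last two rows.

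**Step 2. Inputs for the size.**
- Cohorts of 100 FEVAR and 120 BEVAR (Protocol 4.1).
- Goal 77%, one-sided alpha 0.025, exact binomial (Protocol 10.1; SAP 2.4).
- A 10% allowance for missed visits (Protocol 10.4.3). I assume that all of it is used: 100 × 0.9 = 90 and 120 × 0.9 = 108 evaluable.
- The anticipated rates and power are redacted, so the cohort sizes cannot be reproduced.
- k, the number of deaths in the gap per cohort, is not in the documents. I use 0 to 3 as an assumption; zero is possible.

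**Step 3. The bar.** The p-value for r patent out of n is the sum over x = r to n of C(n,x) · 0.77^x · 0.23^(n−x).
- FEVAR: 77/90 gives 0.031 and 78/90 gives 0.0159, so the bar is 78 (86.7%).
- BEVAR: 91/108 gives 0.042 and 92/108 gives 0.0242, so the bar is 92 (85.2%).

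**Step 4. Put k deaths back as failures, with the patent count held at the bar.**

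| k | FEVAR | p | BEVAR | p |
|---|---|---|---|---|
| 0 | 78/90 | 0.0159 | 92/108 | 0.0242 |
| 1 | 78/91 | 0.0275 | 92/109 | 0.0382 |
| 2 | 78/92 | 0.0448 | 92/110 | 0.0577 |
| 3 | 78/93 | 0.0693 | 92/111 | 0.0837 |

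**Step 5. The same with one more patent patient and k = 1.** FEVAR 79/91 gives p=0.0140 and BEVAR 93/109 gives p=0.0216. Both still pass.

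**Step 6. Effect on the error rate.** Suppose true patency, with these deaths counted as failures, is exactly 77%. Among the m analysed the rate is then 0.77 × (m + k)/m; for FEVAR with k = 2 this is 0.77 × 92/90 = 0.787. The chance of reaching the bar is:

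| k | FEVAR (m = 90) | BEVAR (m = 108) |
|---|---|---|
| 1 | 0.025 | 0.036 |
| 2 | 0.038 | 0.051 |
| 3 | 0.057 | 0.073 |

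The nominal level is 0.025.

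**The case against.** **The early-failure rule and the events committee may already cover this.** The SAP counts loss of patency before 15 months as failure and does not repeat the imaging condition there. An independent committee reviews endpoint-related events. Redacted text follows that rule, and the committee charter is not among the documents. This stands as a reason to check first. It does not close the gap, because the visible rule relies on a defined term that omits autopsy and operative findings, and no visible text lets the committee go beyond it.

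**The effect is a knife-edge.** One death matters only if the count lies exactly on the bar. For true rates that would give 80% to 90% power (an assumption: 88.9% to 90.2% for FEVAR, 87.4% to 88.7% for BEVAR), the chance of exactly 78/90 is about 7% to 10%, and of exactly 92/108 about 6% to 9%. That is before allowing for the chance that such a death occurs at all. This stands, and it limits the size.

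**Like-for-like comparison.** The definitions follow a reporting standard and the goal is derived from literature. A wider failure definition against an unchanged 77% may loosen that comparison. This is a fair cost, and a reason to show the result with and without these deaths.

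**Stronger readings that the documents do not support.** A reader might infer that every loss of patency needs imaging; the procedure route needs none, so an occlusion treated at surgery already counts. A reader might infer that these deaths are used only for instability; they can also count in aneurysm-related mortality and 30-day major adverse events. A reader might want every branch-related death counted as a patency failure; that group includes endoleak and rupture, and interventions for endoleak or disconnection are expressly not loss of primary patency. Nor do the documents show that the worst failures are the likeliest to be missed.

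**Conclusion.** The concern holds in a narrow form. Under the visible text, a death from target-vessel or stent occlusion before any window imaging, shown only at autopsy or at surgery without a procedure on the stent or vessel, is left out of the primary test. The direction is known: it favours the device.

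The size is uncertain and probably small. With 90 and 108 evaluable, one such death reverses a result exactly on the bar in either cohort and does not reverse a result one patient above it. Two or three would lift the error rate at a true 77% to between 0.038 and 0.073. These figures rest on the assumed evaluable numbers and on an assumed count of deaths. The conclusion also assumes that neither the redacted SAP text nor the committee charter already classifies these cases. The repair is cheap and should be made.

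**What to change.** 1. Confirm whether the redacted SAP text or the committee charter already says how an occlusion without listed imaging is classified. If so, state it in the SAP.
2. If not, add to the occlusion definition in Protocol 3.4.1 and SAP Table 1: or autopsy, explant or operative finding, as adjudicated by the Clinical Events Committee.
3. Before the primary analysis, specify one sensitivity run of the same exact test in each cohort. Count committee-adjudicated deaths due to target-vessel or stent occlusion before 15 months as failures, whether or not imaging exists. Leave out deaths from endoleak or disconnection with a patent stent.
4. Report the number of such deaths per cohort beside the primary result.

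The cost is one phrase in two documents, a line in the committee charter and one extra run. It needs no new procedures on patients. The evidence will be incomplete, because autopsy reports are sought only when possible and explants are requested only in the prospective phase. The downsides are a small departure from the reporting-standard wording on which the goal may rest, and possibly a slightly lower patency figure.
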